## 9. DATA MANAGEMENT AND STATISTICAL ANALYSIS

Each participant will be assigned an anonymous ID. Data will be collected using touchscreen laptop computer, and the REDCap (Research Electronic Data Capture) system, a secure web-based application that is designed to support data capture for research studies.

All data analyses will be performed using SPSS 24.0. All estimates will be obtained along with 95% confidence intervals.

Descriptive statistics: All data with approximately symmetric distributions will be described by their mean and standard deviation, as well as number/frequency and percentage (for Aim 3) and variables with skew will be described by the median and interquartile range. Categorical variables will be shown as total number and proportion and will include: race, sex, NYHA functional class, and comorbidity. Associations between categorical variables will be tested by the Chi Square test ( $X^2$ ) or McNemar's test. Continuous variables will include symptom burden, PROMIS depression, fatigue, and sleep disturbance, HRQOL, cardiac function, serum vitamin C levels and biomarker for oxidative stress. Associations between categorical and continuous variables will be tested by t-test and analysis of variance (ANOVA). Associations between continuous variables will be tested using Pearson's correlation coefficient ( $r$ ) will be used to establish if the correlation coefficient is statistically different.

Efficacy analysis for the specific aims is described below:

The primary endpoint is serum vitamin C level. For Aim 1 to test the effect of a vitamin C supplementation intervention on the primary outcome (serum vitamin C level) from baseline to 3-month follow-up among 3 groups, we will use repeated measure of ANOVA to detect differences in the serum vitamin C level from baseline to 3-month follow-up in the intervention group and compared to the control group from baseline to 3-month follow-up.

The secondary endpoints are symptom burden, HRQOL, cardiac function, and oxidative stress. For Aim 2 to test the effect of a vitamin C supplementation intervention on the secondary endpoint of HF symptom burden from baseline to 3-month follow-up among 3 groups, we will use repeated measure of ANOVA to detect differences in symptom burden from baseline to 3-month follow-up in the intervention group and compared to the control group from baseline to 3-month follow-up. Similarly, to test the effect of a vitamin C supplementation intervention on the secondary endpoint of HRQOL (cardiac function, and oxidative stress) compared to the control group, we will use repeated measure of ANOVA to detect differences in HRQOL (cardiac function, and oxidative stress) from baseline to 3-month follow-up in the intervention group and compared to the control group from baseline to 3-month follow-up.

Similar analysis will be done for adverse events. to test the effect of a vitamin C supplementation intervention on the frequencies of adverse events compared to the control group, we will use ANOVA to compare frequencies of adverse events during the 3-month period among 3 groups.

Sample Size and Power: The total sample size of 42 participants will be selected as a pilot feasibility study. With 42 patients (14 in each group) and an alpha level of .05, the power of the ANOVA F test to detect a significant group difference will be 80% if the effect size is 0.5.

Interim/safety Analysis. We plan to conduct the interim/safety analysis when we have 50% of the intervention sample, and the findings (as well as adverse events) will be reported to the medical monitor. The medical monitor will make decisions about the safety of continuing (or stopping) the protocol, providing recommendations for recruitment, retention, safety, and other issues as appropriate.

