### 3. INVESTIGATIONAL PLAN

**Design.** This project is a feasibility pilot study to test the effects of vitamin C supplementation, and to obtain initial estimates of effect size to support a future RCT. The proposed vitamin C supplementation intervention study is a three-group, single blind, placebo controlled prospective design (control n=14, Vit C 500mg n=14, Vit C 1000mg n=14). The most commonly tested dose of vitamin C in current trials on vitamin C supplementation is 1 g/day. The primary endpoint to evaluate the effect of vitamin C supplementation is serum vitamin C level. The secondary outcomes include HF symptom burden, HRQOL, cardiac function, and oxidative stress. The variables would be measured in person at baseline and at 3 months include: HF symptom burden, HRQOL, PROMIS fatigue, depression and sleep disturbance, serum vitamin C level, biomarker of cardiac function (i.e., cardiac output using impedance cardiograph) and oxidative stress (8-iso-PGF2a isoprostane, see below in detail), as well as demographic, clinical, and other variables that can affect study outcomes (e.g., age, gender, race/ethnicity, body mass index, serum creatinine) and medications. HF symptom burden and HRQOL will also be measured at Month 1 and 2 by phone. We will also collect data to assess feasibility (recruitment, retention, attrition rates).

**Sample and Setting.** A total of 42 participants (14 per group) will be randomly assigned to either the control or the intervention group. Patients with HF will be recruited at the University of North Carolina Hospital internal medicine/cardiology outpatient clinics.

**Inclusion/Exclusion Criteria.** Inclusion criteria include patients (a) have a diagnosis of chronic HF. The diagnosis and etiology of chronic HF will be confirmed by a HF cardiologist using established criteria, (b) have undergone evaluation of HF and optimization of medical therapy, (c) are not taking any vitamin C supplementation at all or are willing to stop taking their current vitamin C supplementation, (d) able to read and speak English, (e) have >1 month from any inpatient hospitalization, (e) treating cardiology healthcare provider indicates the individual is a good candidate for this study that involves 3 months of vitamin C supplement of 500 mg/day, 1g/day, or placebo, (f) Per treating healthcare provider's assessment, patient's projected lifespan is greater than or equal to 6 months.

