## 6. CONSENT PROCESS

The consent process includes: 1. Obtain written informed consent from the study subject; 2. Ensure that the most recent version of the IRB-approved consent/HIPAA authorization form is used; 3. Review the informed consent/HIPAA authorization form with the subject in a location that allows privacy; 4. Allow the subject time to read the document and ask questions. Encourage input from family members, if appropriate; 5. Ensure that the subject signs and dates the document in the required sections of the consent and HIPAA authorization form; 6. Ensure the consentor signs and dates (same date) the document in the required section of the consent form; 7. Provide a signed copy of the informed consent/HIPAA form document to the subject; and 8. Document and date consent procedure and file the signed document and checklist back to locked cabinet.

The data (from self-report, impedance cardiograph, and blood drawn) will be collected at baseline clinic appointment and Month 3 in person for all patients. HF symptom burden and HRQOL will be collected at baseline and Month 3, in person and also Month 1 and 2, by phone. All patients will be compensated up to \$50 for participating in this study: \$25 at baseline visit and \$25 at Month 3 visit.

Under special circumstances that we are not allowed to collect in-person data at Month 3 (such as Covid-19 pandemic stay-at-home order that prevents our in-person data collection), we will not collect data from impedance cardiograph or blood drawn. We will only collect self-report data using one of the following 2 ways based on subjects' preference: 1) by phone; 2) by mail-- we will send subjects the questionnaires ahead of time and ask them to complete and send the questionnaire back to us. We also will ask them to send their un-used vitamin C pills back to us by mail.

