## 7. MEASUREMENTS AND STUDY EVALUATIONS

**Serum vitamin C level.** We will measure participant's serum vitamin C level at baseline and Month 3 to measure the effect of vitamin C supplementation. Sample vitamin C will be measured in serum using MyBioSource ELISA kits.

**Symptom burden.** Physical symptom burden will be measured using items from the Memorial Symptom Assessment Scale—Heart Failure (MSAS-HF). The MSAS-HF is an 8-item questionnaire adapted from Portney's Memorial Symptom Assessment Scale that is designed to provide multidimensional information about HF symptoms experienced by patients with HF. Patients will be first asked if the symptom was present during the previous 7 days. If present, three characteristics of each symptom will be rated: frequency of symptom, severity of symptom, and degree of symptom distress. Frequency is rated on a scale from 1 to 4 (rarely to almost constantly), severity rated on a scale from 1 to 4 (mild to very severe) and distress rated on a scale from 0 to 4 (not at all to very severe). Burden score for each symptom can range from 0 (no burden) to 12 (greatest symptom frequency, severity, and distress). The scale has good reliability, ranges of 0.73-0.92 in patients with HF.

**Health-related quality of life (HRQOL).** The Minnesota Living with Heart Failure questionnaire (MLHFQ) is a measure of HRQOL that assesses the patient's perceptions of the

influence of HF on physical and emotional aspects of life. The 21 items are summed with higher scores indicating worse HRQOL. The questionnaire has been widely used to measure quality of life in this population. Researchers have demonstrated evidence for validity and reliability (Cronbach's alphas ranging from .88 to .93). The MLHFQ was used in our study that demonstrated a significant relationship between vitamin C deficiency and HRQOL, as well as between HRQOL and re-hospitalization or mortality.

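### Baseline-adjusted ANCOVA would usually give tighter estimates than the planned repeated-measures ANOVA for the three outcomes measured only at baseline and Month 3, at no extra data cost

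*Combined protocol and SAP*

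**What the plan says.** Section 9 plans repeated-measures ANOVA for the primary endpoint: "we will use repeated measure of ANOVA to detect differences in the serum vitamin C level from baseline to 3-month follow-up". It plans the same for cardiac function and oxidative stress: "we will use repeated measure of ANOVA to detect differences in HRQOL (cardiac function, and oxidative stress) from baseline to 3-month follow-up". It does not say which term of the model is the test, and no efficacy model there includes a baseline covariate.

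Section 7 has the investigators measure "serum vitamin C level at baseline and Month 3 to measure the effect of vitamin C supplementation". Section 6 fixes the timing of the other two outcomes: "impedance cardiograph, and blood drawn) will be collected at baseline clinic appointment and Month 3 in person for all patients". Each of the three therefore has exactly two measurements. Symptom burden and HRQOL are also collected by phone at Months 1 and 2 (Section 3), so this point does not cover them.

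The sample size paragraph says that "the power of the ANOVA F test to detect a significant group difference will be 80% if the effect size is 0.5". One stated purpose in Section 3 is "to obtain initial estimates of effect size to support a future RCT", and Section 9 promises that "All estimates will be obtained along with 95% confidence intervals".

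**The concern.** With only a baseline and one follow-up value, the group-by-time test compares mean change scores. A change score subtracts the whole baseline value, however weakly baseline predicts Month 3. ANCOVA estimates how much of the baseline to remove and is usually more precise when the arms are randomised.

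The pilot has 14 patients per arm and is meant to supply effect-size estimates with intervals for a later trial. Interval width on the primary endpoint bears directly on that purpose, and the baseline values needed to reduce it are already being collected.

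**Working it through.** **Inputs from the documents.** Three arms of 14 (N = 42), alpha 0.05, effect size 0.5, stated power 80% (Section 9).

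**Assumptions, because the documents are silent.** rho, the correlation of baseline with Month 3, is 0.3, 0.5 or 0.7. s, the Month 3 SD divided by the baseline SD, is 0.67, 1, 1.5 or 2. Both are taken as the same in every arm.

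**1. The plan's own figure.** Read 0.5 as Cohen's f in a one-way ANOVA. The noncentrality is 42 × 0.5² = 10.5 on 2 and 39 df, and power is 0.803, so the 80% reproduces. Read as a standardised mean difference, 0.5 gives only 26.2% for a pairwise test and 19.0% to 24.1% for the three-group F test.

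**2. Error variances, in units of the baseline variance.**
- Change score: 1 + s² − 2·rho·s
- ANCOVA: s²(1 − rho²)
- Difference: 1 − 2·rho·s + rho²s² = (1 − rho·s)²

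In large samples the saving cannot be negative and is zero only when rho·s = 1. At N = 42, estimating the slope multiplies the ANCOVA contrast variance by about 1 + 1/37 = 1.027, and error df fall from 39 to 38. A small net loss is therefore possible when rho·s is near 1.

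**3. Worked case, s = 1 and rho = 0.5.** Change: 2 × (1 − 0.5) = 1.00. ANCOVA: 1 − 0.25 = 0.75. The ratio is 0.75, or 0.75 × 1.027 = 0.77 with the slope allowance. The square root of 0.77 is 0.88, so the interval is about 12% narrower.

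**4. Range.** Each cell gives the large-sample variance ratio (ANCOVA/change), then the simulated mean CI-width ratio (14 per arm, normal data, 4,000 trials per cell).

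| s | rho = 0.3 | rho = 0.5 | rho = 0.7 |
|---|---|---|---|
| 0.67 | 0.39; 0.633 | 0.43; 0.666 | 0.45; 0.680 |
| 1 | 0.65; 0.817 | 0.75; 0.877 | 0.85; 0.935 |
| 1.5 | 0.87; 0.946 | 0.96; 0.995 | 1.00; 1.013 |
| 2 | 0.96; 0.991 | 1.00; 1.014 | 0.93; 0.978 |

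**5. Power at s = 1, with the slope allowance.** The plan does not say which SD its effect size refers to, so both readings are shown.

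| f = 0.5 relative to | Test | rho = 0.3 | rho = 0.5 | rho = 0.7 |
|---|---|---|---|---|
| Month 3 SD | Planned | 65.1% | 80.3% | 95.9% |
| Month 3 SD | ANCOVA | 83.0% | 89.8% | 97.8% |
| Change SD | Planned | 80.3% | 80.3% | 80.3% |
| Change SD | ANCOVA | 93.7% | 89.8% | 85.6% |

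A separate simulation (20,000 trials per setting) gave 80.4% v 89.6% at rho = 0.5 on the Month 3 scale, with ANCOVA type I error of 4.9% to 5.2%.

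**6. Unnamed test term.** If the group main effect were read as the test, simulated power at rho = 0.5 would be about 34%, because averaging Month 3 with baseline dilutes the effect.

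**The case against.** The strongest reply is that this is a preference between two valid analyses in a 42-patient feasibility pilot. Repeated-measures ANOVA already uses the baseline, and the stated power is correct for it. That stands: the point is an efficiency improvement, not a defect.

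Second, the gain is unknown. Supplementation is meant to move serum vitamin C and may widen its spread, where the table shows little or nothing to gain. It may also do so only in the active arms, whereas the tables assume one covariance structure. Further simulations allowed for this. With Month 3 SDs of 1, 1.5 and 2 times baseline across the arms, CI-width ratios for 1 g v placebo were 0.95, 1.00 and 1.01 at rho 0.3, 0.5 and 0.7. Type I error over the unequal-SD cases was similar for both methods (ANCOVA 0.051 to 0.062, change 0.051 to 0.059). With different baseline slopes and residual SDs by arm, ANCOVA intervals were 1.3% wider at 14 per arm and 2.2% wider at 9 per arm. In a case with no baseline slope in the active arms they were 27% narrower. The 1.4% worst loss thus belongs to the table's range only, but the losses found outside it were also small.

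Third, Section 9 also asks about change within the intervention group, which a between-arm ANCOVA does not report. That is fair, and the fix keeps it.

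Finally, ANCOVA does not recover Month 3 blood or impedance data missed when in-person visits are barred (Section 6).

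**Conclusion.** The concern holds as a recommended improvement with an asymmetric pay-off. With equal SDs, simulated intervals narrow by 6.5% to 18% for rho from 0.7 down to 0.3. With a smaller Month 3 SD (s = 0.67) they narrow by 32% to 37%. With a larger one (s = 1.5 or 2) the result runs from 5.4% narrower to 1.4% wider. With equal SDs and the slope allowance, the variance advantage lasts until rho reaches about 0.95.

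These sizes rest on assumed SDs and correlations and, in the main tables, on normal, complete data with the same covariance in each arm. The direction does not depend on a particular rho: under a common covariance, ANCOVA is never less precise in large samples. Naming a single model and contrast also settles which term is the test.

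**What to change.** In Section 9, for serum vitamin C, cardiac output and 8-iso-PGF2a, replace repeated-measures ANOVA as the between-arm analysis with ANCOVA. The Month 3 value is the outcome, randomised arm (three levels) the factor, and the baseline value of the same measure the covariate. Report adjusted between-arm differences with the 95% confidence intervals already promised. Keep within-arm change, with its interval, as a descriptive result.

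Because Month 3 spread may differ by arm, plan a residual check and a robust standard error as a sensitivity analysis. State that the 0.5 in the power paragraph is Cohen's f, and on which SD scale. Fix the model before unblinding.

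The cost is about one paragraph and one error degree of freedom (38 instead of 39). It needs no extra patients, visits or assays, and SPSS is already the planned software.

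Symptom burden and HRQOL, with their Month 1 and 2 calls, are outside this change.

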## **2. STUDY OBJECTIVE**

The purpose of this study is to test a low-cost, simple vitamin C supplementation intervention, that is, comparing placebo to 500mg/day vitamin C and 1gram/day vitamin C daily to assess feasibility and acceptability of vitamin C supplementation and effects on serum vitamin C level, cardiac function, HF symptoms, and HRQOL. Our specific aim 1 is to test the effect of a vitamin C supplementation intervention on the primary outcome (serum vitamin C level) from baseline to 3-month follow-up among 3 groups (0.5 g, 1 g vitamin C, and placebo).

Specific aim 2 is to test the effect of a vitamin C supplementation intervention on the secondary outcomes (HF symptom burden, health related quality of life (HRQOL), cardiac function, and oxidative stress) from baseline to 3-month follow-up among 3 groups. Specific aim 3 is to collect data to assess feasibility (recruitment, retention, attrition rates).

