## **5. PROCEDURES AND RECRUITMENT STRATEGY**

Permission for this study will be obtained from the University of North Carolina at Chapel Hill Institutional Review Board. A dedicated and trained research assistant will recruit HF patients from the UNCH clinics. A list of HF patients who will come to the UNCH clinics will be generated and obtained from the staff in charge for the scheduling information in the clinics one week before patients' visits. On the day that the potential participants come to the clinic, the research assistant will screen the potential participant's eligibility based on inclusion and exclusion criteria. The research assistant also will consult with the potential participant's treating healthcare provider to make sure the potential participant is appropriate for the study and patient's projected lifespan is greater than or equal to 6 months. Once the research assistant confirms the potential participants are eligible and gets approval from the provider, the research assistant will approach and briefly explain the study to recruit potential participants while they wait to see their physicians. If potential participants are interested in participation, the research assistant will then confirm eligibility. For eligible patients, study requirements will be explained in detail. If the patient agrees to participate, a signed informed consent will be obtained based on consent process (see below) and we will administer the survey, measure cardiac impedance and obtain the blood samples. All eligible patients will be randomized to either the control group or to the intervention group using the Medsharing application for clinical trials.

**Baseline visit.** Data on socio-demographics, clinical characteristics medications, symptom burden, PROMIS depression, fatigue, and sleep disturbance, HRQOL, will be collected at the beginning of the visit and blood will be drawn to measure serum vitamin C level and oxidative stress (8-iso-PGF2a isoprostane). All participants will be asked to return their respective supplementation bottles to the research assistant at Month 3. We will count pills to determine patient adherence to taking the placebo or vitamin C supplementation.

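### The Aim 1 and Aim 2 analysis sentences mix a three-group test with an intervention-versus-control comparison, and no dose-versus-placebo difference is prespecified

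*Combined protocol and SAP*

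**What the plan says.** Section 2 gives the purpose as "comparing placebo to 500mg/day vitamin C and 1gram/day vitamin C daily", and Aim 1 there lists the three groups by dose. Section 3 fixes the arms as "control n=14, Vit C 500mg n=14, Vit C 1000mg n=14" and says the pilot should "obtain initial estimates of effect size to support a future RCT".

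The randomisation sentences are worded for two groups. In Section 3 participants "will be randomly assigned to either the control or the intervention group", although the same sentence gives 14 per group for a total of 42. In Section 5, "All eligible patients will be randomized to either the control group or to the intervention group".

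In Section 9 the Aim 1 sentence names three groups and repeated-measures ANOVA, then defines the differences to be detected as those "in the intervention group and compared to the control group from baseline to 3-month follow-up". The Aim 2 sentence on symptom burden has the same structure. The next sentence, for HRQOL, cardiac function and oxidative stress, mentions only the intervention group and the control group.

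The power statement, also in Section 9, takes three arms of 14 and a 5% significance level, and says that "the power of the ANOVA F test to detect a significant group difference will be 80" per cent for an effect size of 0.5. The section promises 95% confidence intervals for all estimates but does not list the estimates. It names no dose-versus-placebo contrast, follow-up test or multiplicity rule.

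**The concern.** A three-group F test on 2 degrees of freedom and a contrast of pooled active arms against placebo are different tests with different power. The analysis sentences can be read as either, so the choice could be made after the data are seen, and only one of the two is the test that was powered.

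The larger issue does not depend on which reading is right. A significant 2-df F test says that the three means are not all equal. A significant pooled contrast says that the average of the two doses differs from placebo. Neither says whether 500 mg or 1000 mg differs from placebo, or by how much. A later trial would need those two differences and their precision to choose an arm and a sample size.

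**Working it through.** **Inputs from the plan.** Three arms of 14, N = 42 (Sections 3 and 9); alpha 0.05, effect size 0.5, power 80%, ANOVA F test (Section 9); serum vitamin C measured at baseline and Month 3 (Section 7).

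**Assumptions.** The plan does not name the effect-size metric; I take 0.5 as Cohen's f. It gives no group means; the patterns in step 3 are mine, in SD units, each scaled to f = 0.5.

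**1. The plan's own figure.** Noncentrality λ = N·f² = 42 × 0.25 = 10.5. With F(2, 39) and a critical value of 3.24, power is 80.3%. This reproduces the stated 80%. Other readings of 0.5 do not: f = 0.25 gives 26.7%, a standardised difference of 0.5 with 14 versus 14 gives 24.7%, and the same difference with 28 versus 14 gives 32.0%. The power statement therefore belongs to the three-group test.

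**2. Is the three-group repeated-measures test the powered one?** With two time points, the group-by-time F equals the one-way F on change scores, df (2, 39). So it is, provided f is in units of the change-score SD. If f is instead in Month 3 SD units with no baseline difference, λ = 10.5 / [2(1 − ρ)], where ρ is the baseline to Month 3 correlation, which the plan does not state:

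- ρ = 0.3: λ = 7.5, power 65%
- ρ = 0.5: λ = 10.5, power 80%
- ρ = 0.7: λ = 17.5, power 96%

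**3. Pooled and single-dose contrasts.** All use the three-arm error term on 39 df, two-sided 0.05, unadjusted.

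- Pooled: λ = d² / (1/28 + 1/14) = d² × 28/3, where d is the mean of the two active arms minus placebo.
- Single dose: λ = d² / (1/14 + 1/14) = 7d².

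| Assumed means (placebo, 500, 1000) | Three-group F | Pooled vs placebo | 500 mg vs placebo | 1000 mg vs placebo |
|---|---|---|---|---|
| Plateau (0, 1.06, 1.06) | 80.3% | d = 1.06, λ = 10.5: 88.5% | λ = 7.875: 78.1% | λ = 7.875: 78.1% |
| Equal steps (0, 0.61, 1.22) | 80.3% | d = 0.92, λ = 7.875: 78.1% | λ = 2.625: 35.2% | λ = 10.5: 88.5% |
| Only 1000 mg works (0, 0, 1.06) | 80.3% | d = 0.53, λ = 2.625: 35.2% | no effect: 5% | λ = 7.875: 78.1% |

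The three-group power is the same in each row because f is fixed. The pooled power is not, and can lie above or below 80%. Separate two-sample tests on 26 df give single-dose figures about one point lower (77.1%, 34.5%, 87.7%).

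**4. Precision of each dose difference.** The standard error is SD × √(2/14) = 0.378 SD.

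- Unadjusted half-width: t(0.975, 39) = 2.023, and 2.023 × 0.378 = 0.76 SD.
- Dunnett half-width for two comparisons with a common control: critical value 2.295, and 2.295 × 0.378 = 0.87 SD.
- Ratio: 2.295 / 2.023 = 1.13, so about 13% wider.

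**The case against.** The strongest reply is that the singular intervention group is shorthand for both active arms. Section 4 describes participants in the intervention group as taking one tablet of either dose, and the same section also uses the plural. The adverse-event paragraph in Section 9 speaks of comparison with control and then applies ANOVA to three groups. Nothing in the documents says that doses will be pooled. The Aim 1 sentence itself names three groups, and on that reading analysis and power agree.

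Most of this stands, and it limits the point in three ways.

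- A reader might infer that the planned test is not the one powered at 80%. That follows only on the pooled reading, which the text allows but does not state.
- A reader might infer that patients will be randomised to two groups. The Section 3 sentence gives 14 per group out of 42, and 42/14 = 3; the arm sizes are listed in the same section. This is loose wording.
- A reader might infer that no dose effect will be estimated. Three arms are kept and intervals are promised for all estimates, so the differences can be obtained. What is missing is their prespecification.

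It can also be said that a feasibility pilot needs no formal follow-up tests. That weakens the case for strict multiplicity control, but not the case for naming the differences, because the pilot's purpose is to supply effect sizes.

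**Conclusion.** The concern holds as an inconsistency and an omission. The analysis sentences can be read as a three-group test, which agrees with the stated 80% (80.3%), or as a pooled comparison, which does not (35.2% to 88.5% across the patterns tried). The three-group reading is the more natural one for Aim 1. The text gives least support to it for HRQOL, cardiac function and oxidative stress, where three groups are not mentioned.

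Under both readings no dose-versus-placebo contrast is prespecified, so the stated tests do not deliver the comparison that Section 2 sets as the purpose. This matters more than the power figure. With 14 per arm, each dose difference will carry an unadjusted 95% half-width of about 0.76 SD.

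The powers rest on 0.5 being Cohen's f in change-score SD units, on full retention of 42, and on my assumed mean patterns. The finding that no contrast is named rests on none of these. I class this as a cheap improvement; the plan is not wrong as written.

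**What to change.** In Section 9:

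- Name the three-arm group-by-time F test as the single primary test for serum vitamin C, and state that 0.5 is Cohen's f and which SD it refers to.
- Prespecify two differences in change from baseline to Month 3 from the same model, 500 mg minus placebo and 1000 mg minus placebo, each with a 95% confidence interval, for the primary and every secondary endpoint.
- Use Dunnett adjustment for the primary endpoint. For the secondary endpoints of a pilot, unadjusted intervals labelled as estimation are acceptable.
- Use the same three-arm wording in every Aim 2 sentence.

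In Sections 3 and 5, reword randomisation as 1:1:1 to placebo, 500 mg and 1000 mg, in line with the three arms of 14.

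The cost is wording plus two contrasts from a model already planned, with no extra patients, visits or assays. The one statistical price is the wider primary interval, 0.87 instead of 0.76 SD.
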